****Study 2 Develop the Tailored Educational Intervention****

The intervention will be developed based on available research, results from baseline in the present study and staff views about the facilitators and barriers to optimized pediatric pain management of the included units.

The intervention will be a one day seminar for nurses working at the units, with lectures and workshops with main focus on the subjects showing the lowest pediatric pain management competence. In addition, there will be clinical supervision in pediatric postoperative pain management (two or three days per unit). The intervention will be conducted by two experts (nurse and physician) in pediatric postoperative pain management.

After the intervention there will be different reminders every week for the first month, and then every month (in different forms) about pediatric pain management during six months of time.

Study 3 Implementation and Evaluation of the Intervention

Research Questions

Will tailored educational interventions improve nurses' knowledge and attitude to pediatric pain management?

[figure not shown]
Will tailored educational intervention improve nurses' pediatric pain management practice?

After the educational intervention is implemented there will be different reminders. The first month there will be reminders every week, and thereafter every month for six months period of time. The reminders are based on the general pain management practice, pain assessment, pharmacological and non-pharmacological treatment of pain in children with main focus on the subjects showing the lowest pediatric pain management competence at baseline. The reminders will be in different forms (poster, pamphlet, picture, pocket guide etc.) posted in different places at the units (46).

After the intervention there will be an evaluation of the effectiveness of intervention. To evaluate the intervention three different approaches will be used (questionnaire, observation and interview) to collect data about pediatric pain management practices.

Pre-post tailored educational intervention design, with comparison group, measured during three periods; T-1 (baseline - before intervention), T-2 (one month after intervention) and T-3 (six months after intervention).

Table 2: FLOWCHARTS

Sample/Settings

Unique Protocol ID: 2014/7951

Secondary Ids: 2014/878 [Regional Committee for Medical Research Ethics Norway]

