Three of these six units will be randomized (cluster randomized by units) in an intervention group and three in a comparison group. Each unit has about 40-60 nurses, approximately 260 nurses in total.

Data Collection

All nurses at all six units are asked to take part in the study by completing the PNKAS-N questionnaire at T-2 and T-3. Non-participant observational studies will be conducted at four units at T-2. Furthermore, one unit from the intervention group and one unit from the comparison group will be randomly chosen for observational studies at T-3. During each data collection period observations will be carried out for four-hour periods, two weeks per unit (40 hours per unit per occasions, 240 hours in total). Children older than six years who are having surgery at the time of data collection at the same two units will be asked to participate in an interview (20 children from two units) at T-2.

Data Analysis

Descriptive and inferential statistics will be used to analyse quantitative data at each data collection. Regression analyses that accounts for repeated measurements and cluster correlations (within units) will be used for comparisons between data collected at baseline T-1, T-2 and T-3. Content analysis will be used to analyse the children's responses to the interview questions. Supplementary data from the interviews and the observation studies at T-1 and T-2 will be compared to see if the tailored educational intervention improve nurses' pediatric pain management practice and childrens experience of pain assessment (e.g. use of pain assessment tools, use of pharmacological and non-pharmacological treatment of pain).

Ethics:

Ethical research guidelines will be followed (47-52). An approval from the Norwegian Social Science Data Services (NSD) and Regional Committee for Medical Research Ethics (REK South-East) will be obtained. Necessary approval from the hospitals will be obtained. Contact will be established with relevant persons at the units and cooperation on the implementation of the project. The project will be personally presented by the project manager at the relevant departments at baseline. A pilot observational study and two pilot interviews with children will be done before baseline (T-1).

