Date: 14.12.2017

Pediatric Pain Management Practices in Postoperative Units – an Intervention Study

Unique Protocol ID: 2014/7951

Secondary Ids: 2014/878 [Regional Committee for Medical Research Ethics Norway]

Statistical Analysis Plan

Changes in nurses' knowledge and attitudes of pediatric pain management

- Evaluated with "The Pediatric Nurses' Knowledge and Attitudes Survey Regarding Pain Questionnaire - Norwegian version" (PNKAS-N).

Data will be analysed using mixed models with repeated measures with the unit link as the dependent variable is considered continuous. Changes will be assessed as the overall change and changes at T1 (short term) and T2 (long term) adjusted for T0 (baseline). Baseline characteristics of the nurses will be entered as covariates and the study unit will be treated as a random factor. All analyses will be conducted using SPSS.

Nurses pediatric pain management practices in postoperative units

- Evaluated with non-participant observation using a structured observational tool (checklist) and field notes

The observational data will be analysed using NVivo (NVivo11) and Excel (Excel 2016), and frequency counts and proportions were calculated to summarize the data. A content analysis will be carried out on data within the field notes at T1, T2 and T3. Information in the field notes will be examined for common themes. Using NVivo (NVivo11), the researcher will code the data in each of the categories. After the data in the field notes are coded, the researcher will identify recurring themes and compare this to the data from the pain checklists to provide a picture of

current pain management practices. The data will be given to another experienced paediatric nurse who will code the data without any knowledge of the themes identified by the researcher, to minimize researcher bias. After having coded the data the researcher and the second coder will discuss and agree upon the final wording of the themes.

Children's experiences of pain and pain management after surgery

- Measured with Interview with children about postoperative pain using semi-structured interviews with children after surgery

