Content analysis will be used to analyse the children's responses to the interview questions using NVivo (NVivo11) at T1 and T2. Children's responses to the interview questions will be transcribed verbatim by the researcher who conducted the interviews. Using NVivo (NVivo11), the researcher will code the data in each of the categories. After the data in the field notes are coded, the researcher will identify recurring themes and compare this to the data from the pain checklists to provide a picture of current pain management practices. The data will be given to another experienced paediatric nurse who will code the data without any knowledge of the themes identified by the researcher, to minimize researcher bias. After having coded the data the researcher and the second coder will discuss and agree upon the final wording of the themes.

Supplementary data from the interviews and the observation studies at T2 and T3 will be compared to see if the tailored educational intervention improve nurses' paediatric pain management practice and children's experience of pain assessment (e.g. use of pain assessment tools, use of pharmacological and non-pharmacological treatment of pain).

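### The SAP judges improvement in practice and children's experience by comparing T2 with T3, both after the intervention, where the protocol compares T-1 with T-2

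*SAP*

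**What the plan says.** The last paragraph of the SAP, under children's experiences, sets out how the interview and observation data will be used to judge the intervention: "Supplementary data from the interviews and the observation studies at T2 and T3 will be compared to see if the tailored educational intervention improve" nurses' practice and children's experience of pain assessment. The protocol has an almost identical sentence in Study 3, Data Analysis, but with other waves: "Supplementary data from the interviews and the observation studies at T-1 and T-2 will be compared".

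The protocol's design statement for Study 3 makes T-1 the baseline before the intervention and continues with "T-2 (one month after intervention) and T-3 (six months after intervention".

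The SAP uses two sets of labels. For the PNKAS-N questionnaire it assesses "changes at T1 (short term) and T2 (long term) adjusted for T0 (baseline". For the observations it analyses "data within the field notes at T1, T2 and T3". For the interviews it analyses "responses to the interview questions using NVivo (NVivo11) at T1 and T2".

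On what is collected after the intervention, the protocol (Study 3, Data Collection) says "Non-participant observational studies will be conducted at four units at T-2", followed by one unit per arm at T-3. It says that children "at the same two units will be asked to participate in an interview (20 children from two units) at T-2". The T-3 row of the schedule lists the questionnaire and observation, with no interview. Two other places point the other way. Table 1 lists interviews under a joint T-2 and T-3 heading, and the publication plan puts interviews beside T1, T2 and T3 for the evaluation paper. Neither gives a number of children or units for T-3.

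**The concern.** Whether the intervention improves pain management practice is one of the two Study 3 research questions, and observation and interviews are two of the three evaluation approaches. For those two sources, this is the only SAP sentence that says which waves are set against each other to judge improvement. A contrast between one month and six months after the intervention can show whether practice held or faded. It cannot show whether practice improved on what went before.

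Two further problems follow. The sentence asks for interview data at a wave where the schedule has none. And because T1 is the short-term follow-up in the questionnaire section but follows the protocol's numbering elsewhere in the SAP, an analyst could contrast the wrong waves, and a reader could not tell which comparison had been prespecified.

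**Working it through.** **1. Mapping the labels**

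| Time | Protocol | SAP, observations and interviews | SAP, PNKAS-N |
|---|---|---|---|
| Before the intervention | T-1 | T1 | T0 |
| One month after | T-2 | T2 | T1 (short term) |
| Six months after | T-3 | T3 | T2 (long term) |

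The third column is inferred. The SAP lists three observation waves, and the study has only three, so T1 there must be baseline. The interview waves T1 and T2 then match the protocol's T-1 and T-2.

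The protocol's comparison of T-1 with T-2 translates to T1/T2 in the third column and T0/T1 in the fourth. T2/T3 contains no pre-intervention wave in the third column, and in the fourth it includes a wave that is not defined. Relabelling does not bring baseline into the sentence.

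**2. Observations**

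Inputs from the protocol are 40 hours per unit per occasion, six units at baseline (Study 1, Observational Study), and four units at T-2 and two at T-3 (Study 3, Data Collection).

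- T-1: 6 × 40 = 240 hours, the Study 1 total.
- T-2: 4 × 40 = 160 hours.
- T-3: 2 × 40 = 80 hours.
- T-2 plus T-3: 160 + 80 = 240 hours, which reproduces the Study 3 total.

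All six units are observed at baseline, so T-1 and T-2 share four units, with 160 hours per wave. T-2 and T-3 share at most two units, with 80 hours per wave, so at most 80/160 = 0.5 of the matched material. The overlap could be smaller, because the protocol does not say that the T-3 pair is drawn from the four T-2 units.

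**3. Interviews**

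| Place | Interview waves |
|---|---|
| Protocol, Study 1 and Study 3 Data Collection | T-1 and T-2 |
| Protocol, schedule | T-1 and T-2 |
| SAP, interview paragraph | T1 and T2 |
| Protocol, Table 1 | T-1, then a joint T-2/T-3 list |
| Protocol, publication plan | interviews named beside T1, T2, T3 |
| SAP, closing paragraph | T2 and T3 |

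On the schedule, T-1 versus T-2 sets 20 children against 20, and T-2 versus T-3 sets 20 against none. These are the numbers to be asked, not numbers interviewed.

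**4. Could the sentence mean a comparison between arms at each follow-up?**

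It names no arms. For observations the reading is possible. Three units are in each arm, so four units can be chosen in C(6,4) = 15 ways:

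- 1:3 split: C(3,1) × C(3,3) = 3 ways.
- 2:2 split: C(3,2) × C(3,2) = 9 ways.
- 3:1 split: C(3,3) × C(3,1) = 3 ways.

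These sum to 15, so both arms are always present at T-2, though one arm may rest on a single unit. At T-3 it is one unit against one. For interviews at T-3 the reading fails on the schedule.

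**The case against.** The strongest reply is that the sentence does not say T2 is compared *with* T3. It could mean that follow-up data from T2 and T3 are compared with an unstated baseline, with interviews contributing at T2 and observations at both. That would match the post-intervention collection in the protocol and require no T-3 interviews. The SAP is dated December 2017, after the T-3 collection scheduled for September to October 2015, so naming T3 might be a deliberate extension. The baseline material is also coded: field notes at all three waves and interviews at the first two.

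This reading cannot be excluded, but it is strained. The protocol sentence has the same construction, and there the two named waves are plainly the ones contrasted. If baseline is the comparator, the SAP has to say so. A slip in the labels is plausible too, but the documents do not settle it.

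Other points stand and limit the concern. The comparison is supplementary and descriptive, and no sample size, test or error rate depends on it. The evidence on T-3 interviews is lopsided: the specific statements leave them out, Table 1 is an overview, and the publication-plan line is ambiguous shorthand. The missing statement about arms is a gap in the protocol sentence as well. Finally, T-1 versus T-2 for interviews may not be matched by unit, because it is unclear which two units Study 3 means by the same two.

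**Conclusion.** The concern holds and should be fixed. As written, the SAP's comparison over time has no pre-intervention value under any labelling in the documents, departs from the protocol without explanation, and asks for interviews that are not on the schedule. Compared with the protocol's contrast, it at least halves the matched observation material (from four units to at most two) and leaves the interview comparison with data at one wave only.

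These sizes assume that observation runs as planned at 40 hours per unit, that 20 children are obtained at each interview wave, and that the schedule rather than Table 1 governs T-3 interviews.

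Baseline is missing from this sentence, not from the plan. The PNKAS-N model adjusts for baseline, the protocol plans regression on the quantitative data across all three waves, and the publication plan promises data from every measurement point.

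**What to change.** 1. Use the protocol's T-1, T-2 and T-3 throughout the SAP, including the PNKAS-N section.
2. Replace the closing sentence with one along these lines: *Interview and observation data at T-1 will be compared with those at T-2 to describe change after the intervention, with results shown by arm where both arms have data.* For observations, base this on the four units observed at both waves.
3. For interviews, state which units contributed at each wave. The Study 3 wording could refer to the T-3 observation pair or to the pair used at baseline. State the arm of every contributing unit.
4. Keep T-2 versus T-3 only as a description of whether observed practice was maintained. A T-1 versus T-3 description of the two units observed at T-3 may be added. If arms are to be compared at follow-up, say so.
5. Reconcile Table 1 and the publication plan with the schedule on whether T-3 interviews exist.

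The cost is SAP wording and a small correction to two places in the protocol. The T-1 and T-2 data are already planned, so no new collection is needed.
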